6.14.2.1. Common Adverse Events

Common TEAEs are defined as TEAEs that occurred in $\geq 2\%$ (before rounding) of patients in any treatment group including placebo. The number and percentage of patients with common TEAEs will be summarized by treatment using MedDRA PT ordered by decreasing frequency in the baricitinib 2-mg group.

The number and percentage of patients with TEAEs will be summarized by maximum severity by treatment using MedDRA PT ordered by decreasing frequency in the baricitinib 2-mg group for the common TEAEs. For each patient and TEAE, the maximum severity for the MedDRA level being displayed is the maximum postbaseline severity observed from all associated LLTs mapping to that MedDRA PT.

This analysis will be omitted from the final DBL.

6.14.2.2. Serious Adverse Events

Consistent with the International Conference on Harmonisation (ICH) E2A guideline (ICH 1994) and 21 Code of Federal Regulations (CFR) 312.32 (a) (CFR 2010), an SAE is any AE that results in any one of the following outcomes:

- death
- initial or prolonged inpatient hospitalization
- a life-threatening experience (ie, immediate risk of dying)

- persistent or significant disability/incapacity
- congenital anomaly/birth defect

Important medical events that may not be immediately life threatening or result in death or hospitalization but may jeopardize the patient or may require intervention to prevent one of the other outcomes listed in the definition above should be considered as serious. See examples in the ICH E2A guideline Section 3B.

The number and percentage of patients who experienced any SAE will be summarized by treatment using MedDRA PT nested within SOC. Events will be ordered by decreasing frequency in the baricitinib 2-mg group within decreasing frequency in SOC for the final DBL. The SAEs will also be summarized by treatment using MedDRA PT without SOC.

An individual listing of all SAEs will be provided. A listing of deaths occurring during the study will also be provided.

6.14.2.3. Other Significant Adverse Events

Other significant AEs to be summarized will provide the number and percentage of patients who

- permanently discontinued study drug because of an AE or death
- temporarily interrupted study drug because of an AE

by treatment using MedDRA PT nested within SOC. Events will be ordered by decreasing frequency in the baricitinib 2-mg group within decreasing frequency in SOC.

A summary of temporary interruptions of study drug will also be provided, showing the number of patients who experienced at least 1 temporary interruption and the number of temporary interruptions per patient with an interruption. Further, the duration of each temporary interruption (in days), the cumulative duration of dose interruption (in days) using basic descriptive statistics, and the reason for dose interruption will be provided.

A listing of all AEs leading to permanent discontinuation from the study drug or from the study will be provided. A listing of all temporary study drug interruptions, including interruptions for reasons other than AEs, will be provided.

6.14.2.4. Criteria for Notable Patients

Patient narratives will be provided for all patients who experience certain “notable” events prior to data cutoff date for the submission. See compound-level safety standards for list of criteria.

6.14.3. Clinical Laboratory Evaluation

For the categorical laboratory analyses (shift and treatment-emergent low/high), the analysis period is defined as the treatment period plus up to 30 days off-drug follow-up time. The analysis period for the continuous laboratory analyses (eg, change from baseline by time point) is defined as the treatment period excluding off-drug follow-up time.

All laboratory tests will be presented using the International Système (SI) and US conventional (CN) units. The performing central laboratory reference ranges will be used to define the low

and high limits. Key results pertaining to the 4 key hepatic laboratory assessments (alanine aminotransferase [ALT], aspartate aminotransferase [AST], total bilirubin [TBL], and alkaline phosphatase [ALP]) will be included as a separate analysis to address the risk of liver injury as a special safety topic (see Section 6.14.5.1).

There is 1 special circumstance for laboratory values to be derived based on regularly scheduled, protocol-specified analytes. The low-density lipoprotein (LDL)/high-density lipoprotein (HDL) ratio will be derived as the ratio of LDL cholesterol to HDL cholesterol. There are no central laboratory reference ranges for the LDL/HDL ratio.

The following will be conducted for the laboratory analytes collected quantitatively:

- Box plots: Values at each visit (starting from randomization) and change from last baseline to each visit and to last postbaseline measure will be displayed in box plots for patients who have both a baseline and at least 1 postbaseline visit. The last nonmissing observation in the treatment period will be used as the last observation. Individual measurements outside of reference limits will also be displayed using distinct symbols overlaying the box plot. Original-scale data will be used for the display but, for some analytes (eg, immunoglobulins), a logarithmic scale may be used to aid in viewing the measures of central tendency and dispersion. Unplanned measurements will be excluded. Descriptive summary statistics will be included below the box plot, along with p-values resulting from between-treatment comparison in change from last baseline to last observation. An ANCOVA model with explanatory term for treatment and the baseline value as a covariate will be used. These box plots will be used to evaluate trends over time and to assess a potential impact of outliers on central tendency summaries.
- Treatment-emergent high/low analyses: The number and percentage of patients with treatment-emergent high and low laboratory results at any time will be summarized by treatment group. Planned and unplanned measurements will be included. A treatment-emergent **high** result is defined as a change from a value less than or equal to the high limit at all baseline visits to a value greater than the high limit at any time during the treatment period. A treatment-emergent **low** result is defined as a change from a value greater than or equal to the low limit at all baseline visits to a value less than the low limit at any time during the treatment period. The Fisher's exact test will be used for the treatment comparisons.

For laboratory analyte measurements collected qualitatively, a listing of abnormal findings will be provided. The listing will include, but not be limited to, patient identifier (ID), treatment group, laboratory collection date, analyte name, and analyte finding. If needed by the safety physician/scientist, for analytes measured qualitatively, the number and percentage of patients with treatment-emergent abnormal laboratory results at any time will be summarized by treatment. Planned and unplanned measurements will be included. A treatment-emergent abnormal result is defined as a change from normal at all baseline visits to abnormal at any time postbaseline.

The listing of specific reference ranges used in analysis of laboratory data will be provided.

Note that additional analyses of certain laboratory analytes will be discussed in Section 6.14.5.1 for hepatic analytes, Section 6.14.5.2 for analytes related to hematological changes, Section 6.14.5.3 for analytes related to lipids, Section 6.14.5.4 for analytes related to renal function, and Section 6.14.5.5 for creatinine phosphokinase (CPK).

This analysis will be omitted from the final DBL.

6.14.4. Vital Signs and Other Physical Findings

For the categorical analyses (treatment-emergent low/high), the analysis period is defined as the treatment period plus up to 30 days off-drug follow-up time. The analysis period for the continuous analyses (eg, change from baseline by time point) is defined as the treatment period excluding off-drug follow-up time.

Vital signs and physical characteristics include systolic blood pressure, diastolic blood pressure, pulse, weight, and BMI. Original-scale data will be analyzed. When these parameters are analyzed as continuous numerical variables, unplanned measurements will be excluded. When these parameters are analyzed as categorical outcomes and/or treatment-emergent abnormalities, planned and unplanned measurements will be included.

The planned analyses described for the laboratory analytes in Section 6.14.3 will be used to analyze the vital signs and physical characteristics.

This analysis will be omitted from the final DBL.

Table JAIW.6.8 defines the low and high baseline values, as well as the criteria used to define treatment emergence based on postbaseline values. The blood pressure and pulse rate criteria are consistent with the document *Selected Reference Limits for Pulse/Heart Rate, Arterial Blood Pressure (Including Orthostasis), and Electrocardiogram Numerical Parameters for Use in Analyses of Phase 2-4 Clinical Trials Version 1.3* approved on 29 April 2015 as recommended by the Lilly Cardiovascular Safety Advisory Committee.

Table JAIW.6.8. Categorical Criteria for Abnormal Treatment-Emergent Blood Pressure and Pulse Measurement, and Categorical Criteria for Weight Changes for Adults

Parameter (Units of Measure)	Low	High
Systolic Blood Pressure (mm Hg)	≤ 90 (low limit) and decrease from lowest value during baseline ≥ 20 if > 90 at each baseline visit	≥ 140 (high limit) and increase from highest value during baseline ≥ 20 if < 140 at each baseline visit
Diastolic Blood Pressure (mm Hg)	≤ 50 (low limit) and decrease from lowest value during baseline ≥ 10 if > 50 at each baseline visit	≥ 90 (high limit) and increase from highest value during baseline ≥ 10 if < 90 at each baseline visit
Pulse (beats per minute)	< 50 (low limit) and decrease from lowest value during baseline ≥ 15 if ≥ 50 at each baseline visit	> 100 (high limit) and increase from highest value during baseline ≥ 15 if ≤ 100 at each baseline visit
Weight (kilograms)	(Loss) decrease $\geq 7\%$ from lowest value during baseline	(Gain) increase $\geq 7\%$ from highest value during baseline

6.14.5. Special Safety Topics Including Adverse Events of Special Interest

In addition to general safety parameters, safety information on specific topics of special interest will also be presented. Additional special safety topics may be added as warranted. The topics outlined in this section include the protocol-specified AESIs.

In general, for topics regarding safety in special groups and circumstances, patient profiles, and/or patient listings, where applicable, will be provided when needed to allow medical review of the time course of cases/events, related parameters, patient demographics, study drug treatment, and meaningful concomitant medication use. In addition to the safety topics for which provision or review of patient data is specified, these will be provided when summary data are insufficient to permit adequate understanding of the safety topic.

Analysis of adverse events of special interest will be omitted from the final DBL, and results will be based on the integrated summaries.

6.14.5.1. Abnormal Hepatic Tests

Analyses for abnormal hepatic tests will involve 4 laboratory analytes: ALT, AST, TBL, and ALP. In addition to the analyses described in Section 6.14.3, this section describes specific analyses for this topic.

First, the number and percentage of patients with the following abnormal elevations in hepatic laboratory tests at any time will be summarized between treatment groups:

- The percentages of patients with an ALT measurement $\geq 3\times$, $5\times$, and $10\times$ the central laboratory upper limit of normal (ULN) during the treatment period will be summarized for all patients with a postbaseline value and for subsets based on various levels of baseline.
 - The analysis of $3\times$ ULN will contain 4 subsets: patients whose nonmissing maximum baseline value is $\leq 1\times$ ULN, patients whose maximum baseline is $>1\times$ ULN but $<3\times$ ULN, patients whose maximum baseline value is $\geq 3\times$ ULN, and patients whose baseline values are missing.
 - The analysis of $5\times$ ULN will contain 5 subsets: patients whose nonmissing maximum baseline value is $\leq 1\times$ ULN, patients whose maximum baseline is $>1\times$ ULN but $<3\times$ ULN, patients whose maximum baseline is $\geq 3\times$ ULN but $<5\times$ ULN, patients whose maximum baseline value is $\geq 5\times$ ULN, and patients whose baseline values are missing.
 - The analysis of $10\times$ ULN will contain 6 subsets: patients whose nonmissing maximum baseline value is $\leq 1\times$ ULN, patients whose maximum baseline is $>1\times$ ULN but $<3\times$ ULN, patients whose maximum baseline is $\geq 3\times$ ULN but $<5\times$ ULN, patients whose maximum baseline is $\geq 5\times$ ULN but $<10\times$ ULN, patients whose maximum baseline value is $\geq 10\times$ ULN, and patients whose baseline values are missing.

- The percentages of patients with an AST measurement $\geq 3\times$, $5\times$, and $10\times$ the central laboratory ULN during the treatment period will be summarized for all patients with a postbaseline value and for subsets based on various levels of baseline. Analyses will be constructed as described above for ALT.
- The percentages of patients with a TBL measurement $\geq 2\times$ the central laboratory ULN during the treatment period will be summarized for all patients with a postbaseline value and subset into 4 subsets: patients whose nonmissing maximum baseline value is $\leq 1\times$ ULN, patients whose maximum baseline is $>1\times$ ULN but $<2\times$ ULN, patients whose maximum baseline value is $\geq 2\times$ ULN, and patients whose baseline values are missing.
- The percentages of patients with an ALP measurement $\geq 1.5\times$ the central laboratory ULN during the treatment period will be summarized for all patients with a postbaseline value and subset into 4 subsets: patients whose nonmissing maximum baseline value is $\leq 1\times$ ULN, patients whose maximum baseline is $>1\times$ ULN but $<1.5\times$ ULN, patients whose maximum baseline value is $\geq 1.5\times$ ULN, and patients whose baseline values are missing.

Information collected from additional hepatic safety data collection forms will be provided in patient profiles.

Second, to further evaluate potential hepatotoxicity, an Evaluation of Drug-Induced Serious Hepatotoxicity plot using maximum postbaseline ALT divided by ULN versus maximum postbaseline TBL divided by ULN will be created that includes all patients from the safety population (any phase, any medication). Each subject with at least 1 postbaseline ALT and TBL contributes 1 point to the plot. The measurements do not need to be taken at the same blood draw. Symbols will be used to indicate randomized treatment.

When criteria are met for hepatic evaluation and completion of the hepatic safety case reporting form (CRF), investigators are required to answer a list of questions (see compound-level safety standards). A listing of the collected information will be generated together with a graphical patient profile. This includes demographics, disposition, a display of study drug exposure, AEs, medications, and the liver-related measurements over time will be provided for these patients and any additional patients meeting ALT or AST measurement greater than or equal to $5\times$ ULN (on a single measurement) or ALP measurement greater than or equal to $2\times$ ULN (on a single measurement).

6.14.5.2. Hematologic Changes

Hematologic changes will be defined based on clinical laboratory assessments. Common Terminology Criteria for Adverse Events (CTCAE) will be applied for selected laboratory tests, which are described in the compound-level safety standards.

Treatment-emergent laboratory abnormalities occurring at any time during the treatment period and shift tables of baseline to maximum grade during the treatment period will be tabulated. Planned and unplanned measurements will be included. Treatment emergence will be characterized using the following 5 criteria (as appropriate to the grading scheme):

- any increase in postbaseline CTCAE grade from worst baseline grade
- increase to Grade 1 or above at worst postbaseline
- increase to Grade 2 or above at worst postbaseline
- increase to Grade 3 or above at worst postbaseline
- increase to Grade 4 at worst postbaseline

Shift tables will show the number and percentage of patients based on baseline to maximum during the treatment period, with baseline depicted by the most-extreme grade during the baseline period. With each shift table, a shift table summary displaying the number and percentage of patients with maximum postbaseline results will be presented by treatment group for each treatment period within the following categories:

- Decreased: postbaseline category < baseline category
- Increased: postbaseline category > baseline category
- Same: postbaseline category = baseline category

A laboratory-based, treatment-emergent outcome related to increased platelet count will be summarized in similar fashion. Treatment-emergent thrombocytosis as a laboratory-based abnormality will be defined as an increase in platelet count from a maximum baseline value \leq 600 billion/L to any postbaseline value $>$ 600 billion/L (Lengfelder et al. 1998). Planned and unplanned measurements will be included.

A listing of patients with treatment-emergent thrombocytosis may be provided for safety review.

6.14.5.3. Lipids Effects

Lipid effects will be assessed through analysis of elevated total cholesterol, elevated LDL cholesterol, decreased HDL cholesterol, and elevated triglycerides as described in Section 6.14.3 and with TEAEs potentially related to hyperlipidemia.

Categorical analyses will be performed using National Cholesterol Education Program (NCEP) Adult Treatment Panel III guidelines (NCEP 2002), as shown in the compound-level safety standards. The grade-like categories shown in this table are ordered from traditionally most desirable to least desirable for the purposes of these analyses.

Shift tables will show the number and percentage of patients based on baseline to the least desirable category during the treatment period, with baseline depicted by the least desirable category during the baseline period. With each shift table, a shift table summary displaying the number and percentage of patients with the least desirable postbaseline results will be presented by treatment group for each treatment period within the following categories:

- Decreased: postbaseline category more desirable than baseline category
- Increased: postbaseline category less desirable than baseline category
- Same: postbaseline category = baseline category

Treatment-emergent laboratory abnormalities related to elevated total cholesterol, elevated triglycerides, elevated LDL cholesterol, and decreased and increased HDL cholesterol occurring at any time during the treatment period will be tabulated using the NCEP categories shown in the compound-level safety standards.

Treatment-emergent elevated total cholesterol will be characterized as follows:

- increase to categories 'Borderline high' or 'High'
- increase to category 'High'

Treatment-emergent elevated triglycerides will be characterized as

- increase to categories 'Borderline high,' 'High,' or 'Very high'
- increase to categories 'High' or 'Very high'
- increase to category 'Very high'

Treatment-emergent elevated LDL cholesterol will be characterized as

- increase to categories 'Borderline high,' 'High,' or 'Very high'
- increase to categories 'High' or 'Very high'
- increase to 'Very high'

Treatment-emergent abnormal HDL cholesterol will be characterized as

- decreased
 - decrease to categories 'Normal' or 'Low'
 - decrease to category 'Low'
- increased
 - increase to categories 'Normal' or 'High'
 - increase to category 'High'

The percentages of patients with treatment-emergent potential hyperlipidemia will be summarized by treatment group, ordered by decreasing frequency in the baricitinib 2-mg group using a predefined MedDRA list of PTs that is a subset of the narrow scope PTs in the MedDRA SMQ 'Dyslipidemia' (code 200000026) [see compound-level safety standards].

6.14.5.4. Renal Function Effects

Effects on renal function will be assessed through analysis of elevated creatinine.

The CTCAE will be applied for laboratory tests related to renal effects as shown in the compound level safety standards.

6.14.5.5. Elevations in Creatinine Phosphokinase

Elevations in CPK will be addressed using CTCAE criteria as shown in the compound-level safety standards.

A listing of elevated CPK (CTCAE grade of 3 or above) may be provided for medical safety review.

Treatment-emergent adverse events potentially related to muscle symptoms may be analyzed, based on reported AEs. The Muscle Symptoms special search category is a pre-defined MedDRA search criteria list that contains the narrow scope terms from the Rhabdomyolysis/myopathy SMQ (code 20000002) plus selected terms from the Musculoskeletal SOC. These terms are shown in compound-level safety standards.

6.14.5.6. Infections

Infections will be defined using all the PTs from the Infections and Infestations SOC as defined in MedDRA. Serious infection will be defined as all the infections that meet the SAE criteria.

The number and percentage of patients with TEAEs of infections, serious infections, and infections resulting in permanent study drug discontinuation will be summarized by treatment group using MedDRA PTs. The proportion of patients developing skin infections requiring antibiotic treatment will also be summarized in the overview of infections table.

The number and percentage of patients with TEAEs of infections by maximum severity will be summarized by treatment group using MedDRA PTs.

The IR and 95% CI will be calculated for the overall observation time for infections of special interest (serious infections, treatment-emergent herpes zoster, treatment-emergent tuberculosis, treatment-emergent opportunistic infections [OIs]) for the final analysis.

Treatment-emergent infections may be reviewed in context of other clinical and laboratory parameters via a listing (for details, see compound-level safety standards).

The TEAE infections will be further analyzed in terms of OI, herpes zoster, and herpes simplex. A summary of hepatitis B virus (HBV) deoxyribonucleic acid (DNA) monitoring results and association between infection and neutropenia/lymphopenia will also be provided in the context of infections.

Opportunistic Infection

To identify OIs, the following approach will be used to identify the OIs using a list of MedDRA PTs (refer to the compound-level safety standards).

Potential opportunistic infections identified through search approaches will be combined in one list for medical assessment and final classification of whether the case met the modified Winthrop and colleagues (2015) definitions for OI.

A final listing or tabulation of OIs will be provided for the CSR and to assist the composition of patient narratives.

Herpes Zoster

Cases of herpes zoster will be further classified as follows:

- localized or nonmultidermatomal involvement of the primary and/or adjacent dermatomes only

- complicated – documented ocular (cornea or deeper structure; eg, iritis, keratitis, retinitis, etc.) or motor nerve involvement (eg, palsy; postherpetic neuralgia does not meet criteria for motor nerve involvement)
- uncomplicated, localized or nonmultidermatomal cases that are not complicated
- multidermatomal involvement beyond primary and adjacent dermatomes (ie, >3 contiguous dermatomes) or involvement of 2 or more noncontiguous dermatomes
 - complicated-document ocular (cornea or deeper structure; eg, iritis, keratitis, retinitis, etc.) or motor nerve involvement
 - uncomplicated-multidermatomal cases
- disseminated-systemic infection, visceral or widespread cutaneous (eg, ≥ 5 dermatomes or 3 to 4 dermatomes including at least 1 noncontiguous [nonadjacent]).

All herpes zoster cases will undergo medical review to determine the classification as described above.

A summary table of herpes zoster will be provided based on the above classification. The summary table will also include event maximum severity, seriousness, whether resulting in temporary study drug interruption, whether resulting in study drug discontinuation, whether treated with antiviral medication, and event outcome. Of note, in the context of herpes zoster, antiviral medication treatment is defined as medication that was initiated at the event start date, or within 30 days before or after the event start date. The antiviral medication for herpes zoster includes, but is not limited to, aciclovir, brivudine, cidofovir, famciclovir, foscarnet, ganciclovir, penciclovir, valaciclovir, valganciclovir, vidarabine (best presented by J05AB, J05AC, J05AE, and J05AH ATC codes). Medical representatives may review the concomitant medication list prior to database lock and make adjustment of the above list if necessary.

If a patient has more than 1 event of herpes zoster, the event with the maximum severity will be used in these summary tables. If more than 1 event of herpes zoster occurs with the same severity, the event with the longest duration will be used in the summary table.

Herpes Simplex

A summary analysis of herpes simplex will be provided. Herpes simplex will be defined based on MedDRA PT as listed in compound-level safety standards (both narrow and broad terms in the herpes simplex section). The summary table will include event maximum severity, seriousness, whether resulting in temporary study drug interruption, whether resulting in study drug discontinuation, and whether treated with antiviral medication.

If a patient has more than 1 event of herpes simplex, the event with the maximum severity will be used in these summary tables. If more than 1 event of herpes simplex occurs with the same severity, the event with the longest duration will be used in the summary table.

Skin Infections

A summary analysis of skin infections will be provided. Skin infections may be defined based on MedDRA PT (see the compound-level safety standards).

HBV DNA

A listing of patients with detectable HBV DNA postbaseline will be provided.

Hepatitis B virus DNA status postbaseline (not detectable, detectable but not quantifiable [ie, < lower limit of detection (LLOD)], quantifiable [ie, \geq LLOD]) will be summarized by treatment group stratified by baseline HBV serology status, specifically:

- HBsAb+/HBcAb+
- HBsAb-/HBcAb+

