6.14.2. Adverse Events

Adverse events are recorded in the eCRFs. Each AE will be coded to System Organ Class (SOC) and preferred term (PT) using the Medical Dictionary for Regulatory Activities (MedDRA) version that is current at the time of database lock. Severity of AEs is recorded as mild, moderate, or severe.

A TEAE is defined as an event that either first occurred or worsened in severity after the first dose of study treatment and on or prior to the last visit date during the analysis period. The analysis period is defined as the treatment period plus up to 30 days off-drug follow-up time.

A TEAE defined for the final DBL (Week 16 to end of study) is defined as an event that either first occurred or worsened in severity after the Week 16 visit date and on or prior to the last visit date during the analysis period. The analysis period is defined as the treatment period from the Week 16 visit date plus up to 30 days off-drug follow-up time. The baseline severity is defined as the most severity in the baseline period that is between the first dose date and the Week 16 visit date.

Adverse events are classified based upon the MedDRA PT. The MedDRA Lowest Level Term (LLT) will be used in defining which events are treatment-emergent. The maximum severity for each LLT during the baseline period up to first dose of the study medication will be used as baseline. If an event with missing severity is preexisting during the baseline period, and persists during the treatment period, then the baseline severity will be considered mild for determining treatment emergence (ie, the event is treatment-emergent if the severity is coded moderate or severe postbaseline and not treatment-emergent if the severity is coded mild postbaseline). If an event occurring postbaseline has a missing severity rating, then the event is considered treatment-emergent, unless the baseline rating is severe, in which case the event is not treatment-emergent. The day and time for events where onset is on the day of the first dose of study

treatment will both be used to distinguish between pretreatment and posttreatment in order to derive treatment emergence. Should there be insufficient data for AE start date to make this comparison (eg, the AE start year is the same as the treatment start year, but the AE start month and day are missing), the AE will be considered treatment-emergent.

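### The herpes zoster and simplex tables take every attribute from one selected event per patient, so the yes/no rows can undercount patients with repeat events

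*SAP*

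**What the plan says.** SAP Section 6.14.5.6 (Infections) plans one summary table for herpes zoster and one for herpes simplex.

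- **Zoster, content.** Besides the dermatomal classification, "The summary table will also include event maximum severity, seriousness, whether resulting in temporary study drug interruption, whether resulting in study drug discontinuation", and also antiviral treatment and event outcome.
- **Zoster, repeat events.** "If a patient has more than 1 event of herpes zoster, the event with the maximum severity will be used in these summary tables". The tie-break goes by duration: "If more than 1 event of herpes zoster occurs with the same severity, the event with the longest duration will be used in the summary".
- **Simplex, content.** "The summary table will include event maximum severity, seriousness, whether resulting in temporary study drug interruption, whether resulting in study drug discontinuation", and also antiviral treatment.
- **Simplex, repeat events.** "If a patient has more than 1 event of herpes simplex, the event with the maximum severity will be used in these summary tables", with the same tie-break on duration.

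Three other parts of the SAP matter here.

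- **Severity and seriousness.** Section 6.14.2 grades severity: "Severity of AEs is recorded as mild, moderate, or severe". Section 6.14.2.2 defines seriousness by outcome (death, hospitalization and so on), not by grade.
- **Other displays.** Section 6.14.5.6 itself also counts patients with "TEAEs of infections, serious infections, and infections resulting in permanent study drug discontinuation will be summarized by treatment group", by preferred term. Section 6.14.2.2 summarizes SAEs by patient and lists all of them. Section 6.14.2.3 summarizes and lists AE-related permanent discontinuations and temporary interruptions.
- **Scope.** Section 6.14.5 omits the analyses of adverse events of special interest from the final database lock and relies on integrated summaries instead.

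**The concern.** The selection rule suits a severity row: the worst event gives the patient's maximum severity. The same event, however, also decides the seriousness, interruption, discontinuation and antiviral rows, and these do not follow from the grade. A moderate episode can lead to hospitalization while a severe one in the same patient does not. An early severe episode may leave study drug unchanged while a later moderate one stops it. In each case the table shows the patient as not serious, or not discontinued.

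A reader will take those rows as counts of patients who had such an event. Under the rule they count patients whose selected event was of that kind. For serious or treatment-stopping viral infections on an immunomodulating drug, where counts are likely to be low, one patient more or less is visible.

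**Working it through.** The SAP states no figure on this point, so there is none to reproduce. The check is a logical enumeration, followed by a size estimate on declared assumptions.

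**Step 1: does another clause correct the rule?** Section 6.14.5.6 contains no instruction to derive the yes/no attributes across events. Its wording assigns the selected event to the summary tables as a whole, not to the severity row alone.

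**Step 2: enumerate patients with two events.** Inputs: three severity grades (Section 6.14.2), a yes/no flag on each event (say, serious), and which of the two events is longer.

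- All patterns: 3 × 3 severities × 2 × 2 flags × 2 duration orders = 72.
- Patterns with at least one flagged event: 72 × 3/4 = 54.
- Flag lost because the only flagged event is the milder one: 6 unequal severity pairs × 1 flag pattern × 2 duration orders = 12.
- Flag lost because severity is tied and the only flagged event is the shorter one: 3 equal pairs × 1 flag pattern × 2 duration orders = 6.
- Total lost under the SAP rule: 12 + 6 = 18 of 72.
- Lost if a flag counts when any event has it: 0 of 72.

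These are logical possibilities, not expected frequencies. Severe events are more likely to be serious or to stop treatment, so the real share lost should be smaller than the pattern count suggests. The enumeration shows two things. The rule never adds a positive and sometimes removes one, so the error has a single direction. And a third of the losing patterns (6 of 18) come from the duration tie-break, not from severity.

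**Step 3: size, on assumptions.** Section 5 plans about 150 patients per group, hence about 300 on baricitinib. The SAP gives no incidence or recurrence rate, so the following inputs are assumed, for simplex only:

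| Input | Assumed value | Patients |
|---|---|---|
| Have herpes simplex | 5% of 300 | 15 |
| Of these, have repeat events | 20% to 30% | 3 to 4.5 |
| Of these, attribute sits only on the unselected event | 10% to 20% | 3 × 0.1 = 0.3 to 4.5 × 0.2 = 0.9 |

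That is less than one patient per row across both dose groups. No comparable estimate is offered for zoster.

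**Step 4: where else do these events appear?**

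| Attribute | Other display without the one-event rule |
|---|---|
| Serious | Serious infections (6.14.5.6); SAE summary and listing (6.14.2.2) |
| Stopped study drug | Infections leading to discontinuation (6.14.5.6); summary and listing (6.14.2.3) |
| Interrupted study drug | Summary and listing (6.14.2.3) |
| Antiviral treatment | No other summary specified |

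The other summaries work by preferred term. Simplex is defined by a list of several terms, and adding patient counts across terms does not give the number of distinct patients. Among the displays specified in this SAP, the simplex table is the one that gives the pooled count.

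**The case against.** The strongest reply is that this is a reporting choice. The rule is explicit, reproducible and has a tie-break. It describes one index episode per patient, so severity, seriousness, action taken, treatment, outcome and (for zoster) classification all belong to the same event. Deriving attributes over all events could show a patient as both severe and serious when no single event was both. Zoster classification and outcome are not yes/no items and need a selected event in any case. The rule may also be shared with the integrated summaries and the compound-level safety standards, which are not at hand. Repeat episodes should be few, because only Week 16 responders without rescue stay in the study beyond that visit.

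Much of this stands. It justifies keeping the selected event for classification and outcome, and it shows that the change is not wholly free. It does not rescue the yes/no rows. No footnote is planned to tell the reader that they describe a selected event, and the resulting error always runs downward.

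A reader might infer more: that serious or drug-stopping herpes infections drop out of the study report. The documents do not support that, because the displays in Step 4 count or list them without the rule. Nor does a difference between the herpes tables and the general infection table amount to a contradiction in the plan. One pools terms and the other goes term by term, so they need not match row for row, and the stated rule would explain a gap.

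**Conclusion.** The point holds as a local weakness in two descriptive tables. As written, the rule can only undercount patients in the seriousness, interruption, discontinuation and antiviral rows, through lower severity or through the duration tie-break. That follows from the text and needs no assumption.

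The size is uncertain and probably small. It is confined to patients with more than one event of the same type. It affects the Week 16 and safety-update outputs, since these displays are left out of the final lock. The range of 0.3 to 0.9 patients per row rests wholly on assumed rates and applies to simplex only. Except for antiviral use, the information can be recovered from other displays. No efficacy result or overall safety conclusion depends on it. It is a worthwhile improvement, not a fault that must be corrected.

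**What to change.** In Section 6.14.5.6, for both tables:

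1. Report maximum severity over all of the patient's zoster (or simplex) events.
2. Count seriousness, temporary interruption, discontinuation and antiviral treatment as present if any of those events has the attribute.
3. Keep the existing selection rule and tie-break for zoster classification and outcome only.
4. Add a footnote saying which rows are at patient level and which refer to the selected event.

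The cost is a few sentences and a simple change in the derivation. There are two modest downsides. Rows for one patient may combine features of different episodes, which the footnote makes clear. The rule should also be aligned with the integrated summaries so that the two sets of tables stay comparable. For tables already produced, a footnote stating the one-event rule and the number of patients it affects in each row would be enough.
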